1 INTRODUCTION

This Statistical Analysis Plan (SAP) describes the planned statistical analyses to be performed for data from Protocol GDC-695-001, “A Multicenter, Randomized, Double-Blind, Placebo-Controlled, Parallel Group Comparison Study to Determine the Therapeutic Equivalence of GDC 695 and Diclofenac Sodium Gel, 3% in Subjects with Actinic Keratoses.”

This SAP was created using Clinical Protocol GDC-695-001 Version 2.0 dated 26JAN2017, and the Electronic Case Report Forms (eCRF) Version 1.0 dated 14Oct2016.

2 PURPOSE OF THE ANALYSES

The purpose of this SAP is to outline the planned analyses to be completed to support the Clinical Study Report (CSR) for Protocol GDC-695-001. Any post-hoc or unplanned analyses not identified in this SAP will be clearly identified in the CSR.

3 STUDY OBJECTIVES AND ENDPOINTS

The objectives of the study are to evaluate the safety and therapeutic equivalence of GDC 695 to Diclofenac Sodium Gel, 3% and to establish the superiority of the efficacy of these two products over the vehicle gel in the treatment of actinic keratoses (AK).

The primary efficacy endpoint is the proportion of subjects in the PP population with treatment success (“Complete Clearance”) at Day 90 (30 days after completion of 60 days of treatment). Complete Clearance is defined as 100% clearance of all AK lesions (having a count of zero AKs) in the 25 cm² treatment area (face or bald scalp) at the Day 90 visit.

Safety endpoints will include assessment of the severity and frequency of Adverse Events (AEs) and Local Skin Reactions (LSRs).

4 STUDY DESIGN

This is a multicenter, randomized, double-blind, placebo-controlled, parallel group comparison study of GDC 695 and Diclofenac Sodium Gel, 3% (Fougera) in subjects with AKs on the face or bald scalp. Approximately 600 subjects with at least five but no more than 10 clinically typical, visible or palpable, discrete, nonhyperkeratotic, nonhypertrophic, AK lesions, each at least 4 mm in diameter, contained within a continuous 25 cm² treatment area located on the face (excluding the ears) or the bald scalp who fulfill the inclusion/exclusion criteria will be enrolled at approximately 28 sites.

Subjects will be randomized to one of three treatment groups on a 1:1:1 basis as follows:

- GDC 695 (Gage) (diclofenac sodium gel, 3%)
- Diclofenac Sodium Gel, 3% (Fougera) (Reference Product)
- Vehicle gel (Gage)

All subjects will be instructed to apply the assigned test article to the entire 25 cm² treatment area (face [excluding ears] or bald scalp) identified by the investigator at Visit 1. The assigned test article will be applied twice daily, once in the morning and once in the evening, for 60 days to the entire 25 cm² treatment area. The study will consist of a Screening/Baseline Visit, telephone calls at Day 15 and at Day 45, and follow-up visits at Day 30, Day 60, and Day 90 (30 days after completion of 60 days of treatment).

5 STUDY SCHEDULE OF EVENTS

Visit/Contact	Visit 1 Screening/ Baseline	Visit 2 Telephone	Visit 3 Follow- up	Visit 4 Telephone	Visit 5 End of Treatment	Visit 6 End of Study ¹ 30 Days Post- Treatment Follow-up
Day	1	Day 15 (±3 days)	Day 30 (±3 days)	Day 45 (±3 days)	Day 60 (±4 days)	Day 90 (±4 days)
Treatment Period	Test Article Application Twice Daily for 60 Consecutive Days.					
Informed Consent ²	X					
Medical History & Demographics	X					
Concomitant Medications and Therapies / Procedures	X	X	X	X	X	X
Dermatology Exam	X					
Eligibility Screening, Inclusion, Exclusion	X					
Identification of 25 cm ² treatment area (Face or Bald Scalp) - Location & Size	X					
Photography & “Subject Specific” Template ³	X					
AK Lesion Evaluation & Counting	X				X	X
LSR Assessment	X		X		X	X
Adverse Events	X	X	X	X	X	X
Pregnancy Testing ⁴ for WOCBP ⁵	X				X	

¹ Subjects who terminate early shall complete all final visit activities designated at Day 90.

² Subjects may have consent signed and if required wash-out from prohibited medications or treatments within 30 days prior to the Baseline Visit.

³ A Treatment Area Identification Manual will be provided to the sites with instructions on how to perform photography of the treatment area and on how to create the “subject specific” template.

⁴ UPTs must have a minimum sensitivity of 25 mIU β-hCG/mL.

Visit/Contact	Visit 1 Screening/ Baseline	Visit 2 Telephone	Visit 3 Follow- up	Visit 4 Telephone	Visit 5 End of Treatment	Visit 6 End of Study ¹ 30 Days Post- Treatment Follow-up
Day	1	Day 15 (±3 days)	Day 30 (±3 days)	Day 45 (±3 days)	Day 60 (±4 days)	Day 90 (±4 days)
Application Instructions Distributed	X					
Test Article Application Demonstration	X					
Randomization	X					
Subject Diary Distributed	X		X			
Subject Diary Reviewed		X	X	X	X	
Subject Diary Collected			X		X	
Test Article Compliance Check		X	X	X	X	
Test Article Accountability (Test Article Dispensing)	X		X			
Test Article Accountability (Test Article Return)					X	

⁵ WOCBP include any female who has experienced menarche or is 10 years of age or older and who has not undergone successful surgical sterilization (hysterectomy, bilateral tubal ligation, or bilateral oophorectomy) or is not postmenopausal (defined as amenorrhea >12 consecutive months in women 50 years of age or older). Even women who are using oral, implanted, injectable, intravaginal contraceptive hormones, an IUD, barrier methods (diaphragm/cervical cap and spermicidal, condom and spermicidal) to prevent pregnancy, practicing abstinence, or where the partner is sterile and the subject states she is in a monogamous relationship should be considered to be of childbearing potential. Surgical means of sterilization (e.g., vasectomy, tubal ligation) must be a minimum of six months post-procedure to be considered effective birth control.

6 DEFINITIONS

- End of Treatment (EOT): Visit 5/Day 60
- End of Study (EOS): Visit 6/Day 90 or Early Termination Visit
- Study Day: The study day is the day of study relative to the date of randomization (Baseline visit/Day 1).
Study Day = follow-up visit date – randomization date + 1
- Baseline: The baseline assessment is defined as the last non-missing measurement collected at Baseline visit prior to the test article application.

7 CLINICAL EVALUATIONS

7.1 Efficacy Measurements

7.1.1 AK Lesion Evaluation and Counting

AK lesion counts will be performed at Baseline, Day 60/EOT, and Day 90/EOS. At the Baseline Visit (Visit 1) all AK lesions in the 25 cm² Treatment Area, independent of size, will be identified, counted, recorded on the transparency, and measured for size (i.e., diameter). The number and location of AK lesions to be treated that are ≥4 mm in diameter will also be documented at the Baseline Visit. At Day 60/EOT and Day 90/EOS, the number of total AK lesions, independent of size, in the 25 cm² Treatment Area will be counted including Baseline AKs and new AKs; a new AK is defined as a lesion that was not present at Baseline.

The AK clearance rate within treatment area for a subject at post-baseline follow-up visits will be calculated as follows:

$$\left\{1 - \left[\frac{\#AKs \text{ at follow-up}}{\#AKs \text{ at Baseline}}\right]\right\} * 100.$$

Therefore, if the AK count at follow-up visits is 0, the clearance rate will be 100%, i.e., complete clearance of AK lesions.

7.2 Safety and Baseline Measurements

7.2.1 Adverse Events

An AE is defined as any untoward medical occurrence associated with the use of a drug in humans, whether or not considered drug related. A treatment emergent AE (TEAE) is defined as an AE that started on or after the date of the first dose of test article.

Serious adverse events (SAE) are defined as an AE or suspected adverse reaction that in the opinion of either the Investigator or Sponsor results in death, is life-threatening, requires inpatient hospitalization or prolongation of existing hospitalization, results in persistent or significant incapacity or substantial disruption of the ability to conduct normal life functions, or is a congenital anomaly/birth defect, or important medical events defined in the protocol.

The severity of an AE will be recorded as mild, moderate or severe. The relationship between an AE and the test article will be classified as related, possibly related or not related. The AE outcome will be specified as not recovered/resolved, recovered/resolved, recovered/resolved with sequelae, recovering/resolving, fatal, or unknown.

7.2.2 Local Skin Reactions Assessments

At Baseline, Day 30 follow-up, Day 60/EOT, Day 90/EOS, and Unscheduled Visits (if applicable), LSRs will be assessed in the 25 cm² Treatment Area using a four-point ordinal scale of 0 = absent, 1= mild (slight, barely perceptible), 2=moderate (distinct presence) and 3 = severe (marked, intense) for the following:

- Erythema
- Dryness/flaking/scaling
- Burning/stinging
- Erosion/ulceration
- Edema
- Pain (within the last 24 hours)
- Pruritus (itching) (within the last 24 hours)

These LSRs will be collected independently of AEs. LSRs that require medical intervention (e.g. prescription medication) or extend beyond the 5 cm surrounding skin will be documented as AEs.

7.2.3 Dermatologic Exam

A dermatologic examination will be performed at the Baseline Visit.

7.2.4 Laboratory Tests

Urine Pregnancy Tests (UPTs) will be performed on all WOCBP at the Baseline Visit prior to randomization and at the Day 60/EOS visit.

7.2.5 Prior/Concomitant Medications and Concurrent Therapies/Procedures

Details of prior and concomitant medication use and concurrent therapies/procedures will be collected for each subject.

8 STATISTICAL METHODS

8.1 General Considerations

All statistical processing will be performed using SAS[®] Version 9.4 or higher, unless otherwise stated. For continuous variables, descriptive statistics will include the number of subjects with non-missing data (n), and mean, median, standard deviation, minimum and maximum values. For categorical variables, the number and percentage of subjects within each category will be presented. Subject data listings will be sorted by treatment group, study site and subject number. Summaries will be provided as specified below.

8.2 Analysis Populations

8.2.1 Safety Population

The Safety population will include all randomized subjects who received at least one dose of the test article.

8.2.2 mITT Population

The modified Intent-to-Treat (mITT) population will include all randomized subjects who met all inclusion/exclusion criteria, applied at least one dose of test article, and returned for at least one post-baseline evaluation clinic visit (Visits 3, 5 and 6). Randomized subjects who are lost to follow-up after Visit 1, who return for the EOT visit but have not applied any test article, or who are found not to have met the eligibility criteria will be excluded from the mITT population.

8.2.3 PP Population

The per-protocol (PP) population will include all randomized subjects who met all the following requirements:

- met inclusion/exclusion criteria,
- were compliant with the assigned test articles (applied at least 75% and no more than 125% of the expected (120) test article applications, did not miss more than 10 consecutive scheduled applications and have no other evidence of material dosing noncompliance),
- completed the primary endpoint evaluation at Day 90 visit within the designated visit window (± 4 days), and
- had no protocol violations that would affect treatment evaluation.

As exceptions to the above requirements, the following subjects will be included in the PP population as treatment failures if they met the mITT criteria:

- Subjects who are discontinued from the study due to worsening condition that requires alternate or supplemental therapy for the treatment of AK,
- Subjects who are discontinued early from the study due to lack of treatment effect after completing at least four weeks of treatment.

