9.4 Visit 4 (Day 45 ± 3 days): Phone Call

At this visit, the investigator or designee will:

- Query the subject about any changes in health status or any AEs since the last visit. Document in the AE section of the CRF, as appropriate. NOTE: If severe tolerability issues or a material AE concern of any type are noted, the subject may be scheduled for an in-office visit at the investigator's discretion.
- Record any changes in the subject's concomitant medications and therapies/procedures.
- Review the subject diary and test article compliance.
- Remind the subject to continue to apply test article twice daily, once in the morning and once in the evening, to the skin of the 25 cm² treatment area until the next clinic visit and to bring their tube of test article with them to their next clinic visit.
- Confirm the next appointment and instruct subject to not apply the study medication to the treatment area prior to any study visits.

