9.5 Visit 5 (Day 60 + 4 days): End of Treatment

At this visit, the investigator or designee will:

- Query the subject about any changes in health status or any AEs since the last visit. Document in the AE section of the CRF, as appropriate.
- Record any changes in the subject's concomitant medications and therapies/procedures.
- Use the transparency and the Baseline photo as necessary to locate the selected treatment area.

- Perform the AK lesion count as described in [Section 10.1](#), which includes any AKs ≥ 4 mm in diameter, as well as any smaller lesions.
- Perform the LSR assessment as described in [Section 10.2](#).
- Review and collect the subject diary and test article compliance.
- The subject's tube of test article will be weighed and collected.
- Perform a UPT for all WOCBP.
- Confirm the next appointment.

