17.2 Endpoints

17.2.1 Efficacy Endpoints

The primary efficacy endpoint is the proportion of subjects in the PP population with treatment success (“Complete Clearance”) at Day 90 (30 days after completion of 60 days of treatment). Complete Clearance is defined as 100% clearance of all AK lesions (having a count of zero AKs) in the 25 cm² treatment area (face or bald scalp) at the Day 90 visit. All AKs (those present at baseline and new lesions, if any that may develop) independent of size within the 25 cm² treatment area are to be treated and included in the efficacy lesion count for each visit.

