17.3 Statistical Methods

All statistical processing will be performed using SAS® unless otherwise stated.

The Safety population will include all randomized subjects who received the test article. The mITT population will include all randomized subjects who met all inclusion/exclusion criteria, applied at least one dose of test article, and returned for at least one post-baseline evaluation visit. Randomized subjects who are lost to follow-up after Visit 1, who return for the EOT visit but have not applied any test article, or who are found not to have met the eligibility criteria will be excluded from the mITT population. Subjects will be included in the PP efficacy analyses if they met all the inclusion/exclusion criteria, were compliant with the assigned test articles (applied at least 75% and no more than 125% of the expected (120) test article applications) for the specified duration of the study, did not miss more than 10 consecutive scheduled applications, have no other evidence of material dosing noncompliance, and completed the primary endpoint evaluation at the EOS visit within the designated visit window (± 4 days) with no protocol violations that would affect the treatment evaluation. Subjects who are discontinued from the study due to worsening condition that requires alternate or supplemental therapy for the treatment of AK should be included in the PP population as treatment failures if they meet the mITT criteria. Subjects who are discontinued early from the study due to lack of treatment effect after completing at least four weeks of treatment should be included in the mITT and PP population as treatment failures. Subjects discontinued early for other reasons should be excluded from the PP population, but included in the mITT population, using last-observation-carried-forward (LOCF).

Efficacy summaries and analyses will be carried out in the mITT and PP populations. All summaries of safety will be carried out in the Safety population. LOCF will be used to impute missing values for efficacy variables in the mITT population.

Demographic and baseline characteristics will be summarized by treatment group for all analysis populations. The size of the treatment area in cm^2 will be summarized by treatment group for the mITT and PP populations. Frequency counts and percentages will be reported for categorical data. Sample size, mean, standard deviation, minimum, and maximum will be reported for the continuous variables.

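### Should the per-protocol window for the Day 90 count be tied to the end of treatment, given that protocol and SAP print different end-of-treatment windows?

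*SAP*

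**What the plan says.** **Endpoint.** Protocol 17.2.1 sets the primary lesion count "at Day 90 (30 days after completion of 60 days of treatment". SAP 3 and 8.6.1 say the same.

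**PP rule.** Protocol 17.3 requires that the subject "completed the primary endpoint evaluation at the EOS visit within the designated visit window", given there as ±4 days. SAP 8.2.3 matches it: "completed the primary endpoint evaluation at Day 90 visit within the designated visit window", again ±4 days. Neither refers to the date on which treatment ended. SAP 6 supplies the day count: "The study day is the day of study relative to the date of randomization (Baseline visit/Day 1".

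**EOT window.** The heading of Protocol 9.5 reads "Visit 5 (Day 60 + 4 days): End of Treatment", and the protocol synopsis and Schedule of Events agree. The schedule reproduced in SAP 5 prints Day 60 ±4 days.

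**Length of dosing.** SAP 4 states: "The assigned test article will be applied twice daily, once in the morning and once in the evening, for 60 days". Protocol 4 and 6.2 and both schedules also give 60 days. At the Day 45 call, however, Protocol 9.4 has site staff remind the subject to keep applying "to the skin of the 25 cm² treatment area until the next clinic visit", and the next clinic visit is EOT. The same section tells subjects not to apply before a visit. The synopsis adds that EOT should be booked so that treatment lasts, ideally, 60 days.

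**The concern.** Two things look wrong together. First, the SAP says it was built from protocol Version 2.0, yet its EOT window opens four days earlier. A visit on Day 56 to 59 is early under one document and on time under the other.

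Second, the endpoint is worded as time off treatment, but PP entry is judged by time since randomization. If a subject doses up to a late EOT visit, the nominal ±4 days no longer centres on 30 days. The rule could then keep counts taken well short of the intended follow-up and drop counts taken almost exactly on it. Because PP is the primary population for equivalence, this could add noise to the endpoint and cost evaluable subjects.

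**Working it through.** **Inputs.** PP window for the count: Day 90 ±4, so Day 86 to 94 (SAP 8.2.3, Protocol 17.3). EOT: Day 60 to 64 (Protocol 9.5) or Day 56 to 64 (SAP 5). Day 1 is randomization (SAP 6). Compliance: 75% to 125% of 120 applications, and no more than 10 consecutive missed (SAP 8.2.3).

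**The plan's own figure.** 90 − 60 = 30 days, as stated.

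**Accepted interval from the EOT visit to the count.** Shortest = 86 − EOT day; longest = 94 − EOT day.

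| EOT day | Accepted interval (days) | First interval rejected as too long |
|---|---|---|
| 56 (SAP schedule only) | 30–38 | 39 |
| 60 | 26–34 | 35 |
| 62 | 24–32 | 33 |
| 64 | 22–30 | 31 |

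The overall range is 22–34 days under the protocol's EOT window and 22–38 under the SAP's.

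**Where 22 and 31 come from.** Both arise only with EOT on Day 64: 86 − 64 = 22 is accepted, and 95 − 64 = 31 is rejected because Day 95 is outside the window. Both documents allow Day 64, so the +4/±4 mismatch plays no part; it only moves the longest interval from 34 to 38. With EOT on Day 60 the pair reverses: 31 days (Day 91) is accepted and 22 days (Day 82) is rejected.

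**Dependence on the dosing text.**
- Dosing up to a Day 64 visit: 22 accepted, 31 rejected.
- Visit-day dose withheld, last application on Day 63: 86 − 63 = 23 accepted, 95 − 63 = 32 rejected.
- Dosing stops after 60 days whatever the visit date: 86 − 60 = 26 to 94 − 60 = 34, that is about 30 ±4 for everyone.

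**Does the EOT window enter any analysis?** The PP criteria in SAP 8.2.3 are eligibility, compliance, the Day 90 window and absence of violations affecting evaluation. None uses the EOT visit date. Four fewer days is 4 × 2 = 8 applications, or 8/120 = 6.7%. A fully dosed subject stopping after 56 days has 112/120 = 93.3%, far above the 75% limit (90 applications).

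**What a window of 30 ±4 days from the last application would do.** Take a subject who misses the final 10 applications, which is 5 days. The last dose is on Day 55, with 110/120 = 91.7% applied, so the subject is compliant. The window becomes 55 + 26 = Day 81 to 55 + 34 = Day 89. A count exactly on Day 90 would be excluded, and counts on Day 81 to 85, outside the protocol's Visit 6 window, would be accepted.

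**The case for a change.** The strongest case for a change is that the endpoint is worded as time since treatment, so eligibility for the primary analysis ought to be judged on the same clock. For a subject who doses to Day 64, a count exactly 30 days later falls on Day 94, the last permitted day, so the window is in effect −8/+0 days. PP membership should also be unambiguous before unblinding. The excluded-violations criterion gives the mismatch a possible route in, since an EOT visit on Day 57 is a deviation under one document and not under the other. Anchoring on the EOT date would avoid the missed-final-doses difficulty shown above.

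Some of this stands. The windows do differ, the two descriptions of dosing length do not agree, and the arithmetic is right for a Day 64 EOT. The rest is weaker. The violations criterion excludes only departures that would affect evaluation, which is a judgement on the individual case; the protocol governs site conduct, and deviations are listed in any case. Anchoring on EOT would still depart from the PP definition in Protocol 17.3 and the Visit 6 window in Protocol 9.6, so both documents would have to change. Any end-of-treatment anchor also makes PP membership depend on a post-randomization date that tolerability may influence, which a randomization anchor avoids. The present rule applies alike to all blinded arms, and nothing in the documents suggests that visit timing would differ between them.

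**Conclusion.** No change to the analysis follows. The ±4 in the SAP schedule is a clerical slip relative to the protocol on which the SAP says it is based, and it feeds no PP criterion or planned analysis. The two EOT windows, and the two descriptions of how long dosing continues, must be reconciled as text; this review takes no position on which is right.

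The randomization-anchored Day 90 ±4 rule is a fair trade-off, stated consistently in both documents. Its worst case is an interval of 22 days instead of 30, and this requires EOT on Day 64, dosing up to that visit and a count on Day 86. With EOT on Day 60, or with dosing limited to 60 days, the accepted interval is about 26 to 34 days. Moving the anchor to the last application would replace this edge case with another that excludes on-schedule counts from compliant subjects.

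The effect on the equivalence result cannot be calculated, because the documents give no distribution of visit dates and the sample-size inputs are redacted. The judgement that it is minor rests on most EOT visits being held near Day 60, as the synopsis scheduling note intends, and on visit timing being similar across blinded arms.
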